We anticipate 4 to 6 schools will participate in the main study. We will also assess process outcomes, including: recruitment, retention and intervention fidelity, and secondary intervention effects on parent healthy eating and gardening behaviors. Assessments will be conducted in a sample of the elementary school children in grades 3 and 4 at each school and in one of their parents (or other adult caregiver in the household that is the index adult for analysis), at the beginning and the end of the first school year. We use a culturally appropriate tool that includes foods commonly eaten by Navajo people to measure food choices in both children and parents. Choosing fruit and vegetables to eat at meal times in children and gardening participation and self-efficacy in children will be assessed using instruments from other studies. Secondary outcomes include measures of child weight and of academic achievement, as well as parent measures of healthy eating and gardening. Analyses estimating the intervention effect will assess the differential change over the first school year between the two groups of schools, adjusting for school level clustering. After the follow-up evaluation, the delayed intervention group will receive the intervention. A final descriptive assessment will be included at the end of the second school year. Continued engagement and skill strengthening will occur through quarterly parent workshops. Attendance at these will be tracked. This proposal is timely as the Navajo Nation consider their policy on dietary and activity benchmarks for schools as part of a rounded curriculum.

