### **III. RESEARCH APPROACH**

#### **A. Overview and Design**

The small randomized controlled trial of an intensive curriculum and school garden intervention will be implemented in elementary schools in two communities (Shiprock and Tsaile). The study will begin in year 1 with a period of engagement and recruitment of schools in each community; with the goal of recruiting three schools *in each community* to start the run-in phase (see Figure 1). The run-in period will include time for greater engagement with the school community, an assessment of the potential garden site and an assessment of evaluation readiness. Depending on whether all three schools in the community qualify for the study at the end of run-in, or only two schools per community, we will randomize three or two schools to intervention or delayed intervention status in each community. We will have either two intervention schools and 4 delayed intervention schools, or 2 intervention schools and 2 delayed intervention schools, depending on the run-in information. We will conduct baseline data collection (T1) at the beginning of the school year in Year 2

[figure not shown]
with both children and parents. Students in the intervention group will receive the curriculum and school garden during that academic school year. At the end of the school year, we will conduct the T2 assessment in children and parents. The main evaluation period is between T1 and T2, and the statistical analysis methods refer to the T2 versus T1 change in outcome measures (healthy eating and gardening). After that, at the beginning of the next school year (Year 3), the delayed intervention schools will receive the intervention. During Year 3, we will also conduct quarterly community gardening workshops for adult family members in all schools.

Attendance at these will be tracked. A final assessment (T3) will be conducted at the end of the second school year in all the randomized schools to describe behaviors in children and parents over time, using a quasi-experimental design that estimates change in the delayed intervention group between T2 and T3, attributable in part to the delayed intervention.

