## D. School Engagement and Recruitment

Our first aim is to engage and recruit elementary schools from two communities on the Navajo Nation for the randomized control trial of the Yéego! Healthy Eating & Gardening intervention. We recognize that personal interactions with key stakeholders is an essential part of community engagement. This will require the assistance of “key influential” in the school system, faculty educators at Diné College, and local residents who are Navajo members of our research team. Based on our previous experience in recruiting of organizations for group-randomized trials, we plan to implement the following steps to recruit and engage potential schools as research partners. In defining the population of schools from which to recruit, we note there are about 90 elementary schools in the Navajo Division of Education system, including 16 in Shiprock and 11 in Tsaile. We will identify schools in Tsaile and Shiprock who meet the eligibility criteria for the study. The eligibility criteria will include having been in existence for at least three years, school size (have between 40 to 100 students in grades 3 and 4 combined), have more than two-thirds Navajo students and satisfy a garden site checklist that can overcome garden barriers (e.g. have access to water) (Figure 2). Information about potential schools will come from the initial phone screening and a school questionnaire. Each school will be contacted by phone and letter to assess their initial interest in participating in the study. After initial conversations, study staff will arrange a meeting with school faculty meeting to discuss the intervention and study procedures in detail. The meeting will provide detailed information on the student recruitment and data collection process and emphasize efforts to minimize disruption of daily classroom routine. For interested schools, we will also do an initial assessment of the school resources and garden site. From these meetings we hope to identify at least six schools, three in each community for further engagement. Our next phase with the schools will serve as a “run-in” period to the trial. During this time we will hold meetings with teachers and parents, and conduct initial surveys to gauge their level of interest, ability to engage in the types of evaluations used in the main study, and likelihood of engaging fully in the curriculum and school garden intervention. Our goal is to randomize a minimum of four schools (two in each community) that will participate for the duration of the project. If all schools qualify for the study on completion of run-in, we will randomize all six schools, two to intervention and four to delayed intervention.

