Prior to the start of the school year, and after a successful run-in, information regarding the study will be sent out to all families in randomized schools. They will also be invited to attend an information night timed to coincide with a parent orientation or chapter house meeting to learn about the study in detail. Information about the study will also be visible in the school newsletter prior to the start of recruitment, posted on school websites and posters displayed at the school to invite students to participate in the study. The project will ask from the school administration staff the first and last name of students, grade and teacher in order to create individualize recruitment packets. Students will receive a recruitment packet from their teacher to be sent home with their daily schoolwork. The packet will include information about the study, child assent and adult caregiver permission and self-consent to participate in the study. Students will be encouraged to return their packets in one week to be eligible for a school-wide raffle. Raffle for past studies included gift certificates to a local restaurant, movie theatre or activity for the family. The top raffle prizes will be a \$50 gift card for the family, additional prizes include tote bags and backpacks. After the first week, a second round of packets will be distributed to the remaining students to reach the required recruitment goal of 60% of third and fourth grade students. In addition, to compensate teachers for their support of the packet process, classes that reach the 60% enrollment goal will receive \$50 worth of classroom teaching supplies. The teachers will nominate what supplies their classroom will need. Study staff will purchase the items up to \$50 and deliver to the teachers. For the students consented to participate in assessment, study staff will identify a series of after school times for students to complete the baseline survey. Student and adult caregivers who are not able to attend an assessment session after school, will be provided the opportunity to conduct the assessment at their home or place of their choosing. Each student/adult pair completing the assessment will receive a monetary gift in the form of cash, gift card or small gifts for children valued at \$5 (e.g., flashlight, water bottle, cinch-sack/backpack). The starting cash amount for parent survey is \$20 and child is \$5. In order to maximize retention at later time points the survey incentive will increase by \$5 at each time point. Other retention efforts include phone, email and text reminders. A school champion for each school will be assigned by the principal to assist with enrollment and assessment logistics for each school. The champion coordinates times for the assessment team to pick up completed enrollment packets, deliver new packets to teachers and assist with delivery of raffle prizes to schools and families. As a token of appreciation for their assistance, an honorarium of \$100 will be provided at the end of the 2020 and 2021 school year.

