## Student Follow-up Assessment (amended due to COVID-19)

### Preparation

Yéego! Healthy Eating & Gardening project has mailing addresses (including PO Box numbers) for almost all of the 3rd and 4th grade students in all six schools. For those students for whom the study has no address, contact will be made via phone and email requesting mailing address. It is anticipated that we will obtain mailing addresses that will reach ALL the 3rd and 4th grade students.

In addition to the mailed survey, parents/guardians that provided email addresses will be sent an email with a secure link to the follow-up survey. The weblink will send participants to a new virtual server with more restrictive access. The Yeego Server and the process to protect the files stored locally at Fred Hutch was approved by Information Security Office and IRB 08-12-2019.

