## E. Analysis Plan

Two of our four primary outcome measures in children (tendency to choose fruit and vegetables to eat during snacks/meals and gardening self-efficacy) will be measured through questions that use a Likert-type scale with four response options. With numeric codes assigned to each response option, means and standard deviations will be calculated per question and overall. Thus, possible mean values range from one to four. The intention to treat analysis will be a t-test comparing the change in mean values from baseline (beginning of school year at T1) to follow-up (end of school year at T2) in the intervention schools to those changes in mean values in the schools receiving the delayed intervention. This differential change in groups between T1 and T2 is the estimated intervention effect. The estimated effect of the intervention will also be analyzed using linear mixed models with T2 individual outcome as the dependent variable and intervention assignment as the

independent variable, adjusting for T1 individual outcome and school random effect. It will also allow for adjustment for additional covariates (school within intervention group if applicable) and for known or probable individual level confounders. Information from all responding students will be included in the analysis, with adjustment for repeated measures (expected to be the majority of the students). This will assess robustness of inferences from the simpler model. A sensitivity analysis without adjusting for possible intra-school correlations will be performed using linear regression models. In addition, the Akaike Information Criterion will be compared between the simpler model and the theoretically correct multilevel model to check model fit.

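### With four to six schools, an AIC comparison cannot show whether school clustering may be ignored, and the plan does not say what a favourable AIC would mean

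*Combined protocol and SAP*

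**What the plan says.** Schools are the randomised units. Section II gives the number: "We anticipate 4 to 6 schools will participate in the main study". Section III.A gives the allocation: "We will have either two intervention schools and 4 delayed intervention schools, or 2 intervention schools and 2 delayed intervention schools". The COVID-19 amendment to the student follow-up in Section IV.B refers to "grade students in all six schools", so the later text is at six.

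Section IV.E sets out these analyses for the Likert-scale primary outcomes:

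- The intention to treat analysis is a t-test on the T1 to T2 change, with no school term mentioned.
- A linear mixed model of the T2 outcome, adjusted for T1 and with a school random effect, is also fitted, to check the robustness of the simpler analysis.
- "A sensitivity analysis without adjusting for possible intra-school correlations will be performed using linear regression models".
- Finally, "the Akaike Information Criterion will be compared between the simpler model and the theoretically correct multilevel model to check model fit".

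Section II says that the effect analysis will adjust for clustering by school. The documents give no ICC, no significance level, and no statement of what follows if AIC favours the simpler model.

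**The concern.** Randomisation by school settles by design that school belongs in the inferential analysis. A fit statistic is not needed to decide it. An AIC comparison treats clustering as a question the data can answer, and with two or four degrees of freedom between schools the data can hardly answer it. The headline test has no stated school adjustment. If AIC came out in favour of the simpler model and nothing said how to read that, the result could be taken as support for the unadjusted test. At stake is the false-positive rate of the primary comparison.

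The term simpler model is also unclear. Where Section IV.E introduces the mixed model as a robustness check, the simpler model appears to be the change-score t-test. In the AIC sentence it could equally be the unclustered regression described just before. A model of change and a model of T2 have different outcomes, so their AICs are not comparable.

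**Working it through.** The documents give no ICC, power or AIC figure, so there is nothing to reproduce.

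**Inputs from the documents**

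- Schools: k = 4 (2 v 2) or 6 (2 v 4), from Section III.A.
- Children per school: eligibility is "school size (have between 40 to 100 students in grades 3 and 4 combined") in Section III.D. The "required recruitment goal of 60% of third and fourth grade students" in Section IV.B gives 0.6 × 40 = 24 to 0.6 × 100 = 60 per school. Section V.A allows up to 80 enrolled per school, so m runs from 24 to 80.

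**Assumptions**

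- ICC (ρ) of 0.01 to 0.10 for the outcome as analysed; two-sided 5% tests at child level; equal school sizes; no true effect; the two communities not modelled.

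**When AIC prefers the unclustered model.** Let F be the between-school mean square within arms (k − 2 df) divided by the within-school mean square (k(m − 1) df). By maximum likelihood (ML), the likelihood-ratio statistic for the school variance is

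LR = km·ln{[k(m − 1) + (k − 2)F]/(km)} − k·ln{(k − 2)F/k} if F > k/(k − 2), and 0 otherwise.

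The multilevel model has one more parameter, so AIC prefers the unclustered model when LR < 2. Solving LR = 2 at m = 48 gives a cut-off c = 4.78 for four schools and 3.11 for six. The between-school mean square must therefore be about five or three times the within-school one before AIC notices clustering.

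**Probability.** F is distributed as θ times an F variable on k − 2 and k(m − 1) df, with θ = 1 + mρ/(1 − ρ). So P(AIC prefers unclustered) = P(F variable < c/θ).

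- Six schools, m = 48, ρ = 0.02: θ = 1 + 48 × 0.02/0.98 = 1.98; c/θ = 1.57; P = 0.82.
- Six schools, m = 80, ρ = 0.05: c = 3.10; θ = 1 + 80 × 0.05/0.95 = 5.21; c/θ = 0.59; P = 0.33.

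**Error of the unclustered test.** This is approximately 2{1 − Φ(1.96/√D)}, with D = 1 + (m − 1)ρ.

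- m = 24, ρ = 0.01: D = 1.23, error 0.077.
- m = 80, ρ = 0.02: D = 2.58, error 0.222.

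**Results.** Ranges run from m = 24 to m = 80. Simulation with 200,000 trials per setting agrees to within 0.01.

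| ICC | AIC prefers unclustered, 4 schools (ML) | 6 schools (ML) | Type I error of unclustered test |
|---|---|---|---|
| 0.01 | 0.98–0.93 | 0.96–0.85 | 0.08–0.14 |
| 0.02 | 0.96–0.83 | 0.92–0.68 | 0.11–0.22 |
| 0.05 | 0.88–0.60 | 0.76–0.33 | 0.18–0.38 |
| 0.10 | 0.73–0.38 | 0.51–0.13 | 0.29–0.52 |

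Restricted maximum likelihood (REML) lowers the AIC figures: at ICC 0.01 to 0.02 they span 0.54 to 0.92 over all settings. The ML probability falls to one half at an ICC of 0.068 to 0.198 with four schools and 0.033 to 0.102 with six.

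**Cross-check.** With unequal schools of 24 to 60 children and a T1 covariate (ML, 1,500 trials per setting), the probabilities at ICC 0.01, 0.02, 0.05 and 0.10 are 0.97, 0.93, 0.80 and 0.57 for four schools, and 0.93, 0.85, 0.59 and 0.34 for six.

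**Does a favourable AIC identify the safe trials?** No. With six schools, 48 children and ICC 0.05, the unclustered test rejects in 29.1% of the trials where AIC favours it and in 28.8% of all trials.

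**Comparison.** A t-test on school means rejects in 4.9% to 5.1% of null trials in every setting. If AIC were used to choose between that test and the unclustered one, the error at ICC 0.01 to 0.10 would be 7.4% to 23.0% with four schools and 7.4% to 15.4% with six.

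**The case against.** The strongest reply is that the plan gives AIC no decision role. It describes the comparison as a check of fit, calls the multilevel model theoretically correct in the same sentence, fits that model in any case, and labels the unclustered regression a sensitivity analysis. This stands. A reader might infer that AIC will decide which model is reported, but nothing in the documents says so. The selection error rates above show what such a rule would do; they do not describe the plan. What remains is a missing rule of interpretation beside a headline test with no stated school term.

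Three other strong readings also go too far:

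- **That AIC will usually favour the unclustered model.** This needs an ICC that the documents do not give. With six schools and ICC 0.05, ML-based AIC favours the multilevel model in most trials at 60 to 80 children per school, and with REML at 36 to 80.
- **That the AIC step causes the inflated error.** Conditioning on AIC hardly changes the error. It would remain if the AIC sentence were deleted.
- **That the AICs are certainly not comparable.** If the simpler model is the unclustered regression, fitted to T2 in the same children, they are comparable. The text is ambiguous, and no error is shown on that reading.

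It is also fair to say that an unclustered fit, labelled as such, shows how far the standard error moves when school is included. Removing it is a matter of preference.

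**Conclusion.** The point holds in a limited form. With four to six schools, AIC is too insensitive to show that clustering may be ignored. The clearest case is a small ICC of 0.01 to 0.02, where AIC by ML favours the unclustered model in about 68% to 98% of trials while that test's error is about 8% to 22%. At an ICC of 0.05 or more the direction of the AIC result depends on the number and size of schools, but the unclustered test is worse (18% or more). In neither range does a favourable AIC make that test safe.

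The conclusion rests on assumed ICCs, a child-level reading of the t-test, and a two-sided 5% level. The exact percentages also assume equal school sizes, though the cross-check with unequal schools agrees in pattern. The main weakness is the intention to treat t-test without a stated school adjustment. The AIC comparison adds a risk of misreading and cannot repair that weakness.

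**What to change.** In Section IV.E:

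1. State that inference for the intervention effect, including the intention to treat analysis, rests on a school-level analysis or on a mixed model with school and small-sample degrees of freedom, whatever the estimated school variance or AIC. Keeping a school random effect without the small-sample correction is not enough with four to six schools.
2. Drop the AIC comparison, or report it as description only, between named models of the same outcome fitted to the same children, beside the ICC and its interval.
3. Keep the unclustered regression, if wanted, labelled as descriptive and not used for inference.

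The change takes a few sentences and needs no new data. The cost is wider intervals and larger p-values: the school-level t-test has k − 2 = 2 or 4 degrees of freedom, so its two-sided 5% critical value is 4.30 or 2.78 in place of about 1.96. That loss of precision reflects the number of schools randomised, and the unclustered test only hides it.

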## V. Protection of Human Subjects

### A. Risks to Human Subjects

**Human Subjects Involvement, Characteristics, and Design.** The primary study population is children, both male and female, in grades 3 or 4. One member of their adult family (21 years or older) is included in the secondary study population. Because of the multicomponent nature of the intervention, including the school garden, and parent workshops, participation in the intervention activities will include children in other elementary grades and other parents. The proposed study will take place in elementary schools within the Shiprock, NM and Tsaile, AZ area; both rural areas located within the Navajo Nation. The majority of the

participants in the study will be American Indian (AI), primarily members of the Navajo Nation. It is anticipated that as many as 960 participants will be formally enrolled in the study: 80 3rd and 4th grade students within each of 6 distinct schools (three in Shiprock, 3 in Tsaile), plus one parent/caregiver for each child. Participants will be recruited through the enrolled, participating elementary schools selected.

**Study Procedures, Materials, and Potential Risks.** Schools will be recruited to the study and will take part in a “run-in” including planning with the study, and an evaluation of readiness to complete study surveys. We will recruit from 6 elementary schools in two communities (two schools in Shiprock, NM and three schools in Tsaile, AZ). We will recruit and enroll children in grades 3 and 4 (ages 8-11) who attend the selected elementary schools participating in the proposed study.

Data will be collected for research purposes only. Materials to be obtained include interviewer-administered questionnaires and anthropometric measures (height and weight) at three time points of the proposed study; at the beginning-T1 (August) and end-T2 (June) of the intervention school year and the end of the second school year-T3, once the delayed intervention has completed the intervention. We will assess process evaluation measures including recruitment, retention and intervention fidelity.

The interviewer-administered questionnaires will be completed online with questions constructed from items taken from the IRB approved previous study, “Engaging School and Family in Navajo Gardening for Health” and valid measures adapted minimally to be culturally relevant and understood by children and adult members of the Navajo community. The questionnaire for children will include healthy eating behaviors and gardening participation and self-efficacy including fruit and vegetable consumption at meals, relative frequency of health foods, gardening participation, and gardening self-efficacy. The parent/caregiver questionnaire will include dietary intake questions, fruit and vegetable consumption using the instrument from the 5 A Day study, as well as soda and fast food consumption, obesity related dietary behaviors and gardening frequency measures. Both parent and child will complete a virtual picture sort frequency method following the approached used in our current study. (originally developed in an African American community and modified for this study using foods commonly consumed by Navajo). Weekly frequencies will be converted to a relative healthy food ratio (healthy foods to total foods) based on the Alternative Healthy Eating Index (AHEI) categories.

There are minimal risks associated with participating in the survey assessments. It is possible that some participants (adult or child) may experience discomfort when answering questions about their health behavior. Participants will be informed that they do not have to answer any questions that make them feel uncomfortable. Finally, risks may include feelings of embarrassment, for children, during body measurements (height and weight). All staff will be trained to be aware of such discomfort, how to react in this situation, how to ease participants, and provide outside resources when needed.

As a physical out-door activity, the act of gardening can occasionally produce risks including cuts, scrapes, and sunburn. In most circumstances, accidents occurring in a garden are superficial. When proper precautions are taken (i.e. wearing appropriate footwear, sunscreen, hat, gloves) and training is given on the appropriate use of tools, accidents are usually preventable. Participants will be informed of the risk of out of door activities and advised to wear appropriate clothing, sunscreen and hat and to drink plenty of water.

